### **Randomisation**

We used a web-based trial management system for randomisation. The trial management system concealed group allocation until the randomisation was performed. Participants were randomised in a 1:1 ratio using permuted blocks with random sizes from 4 to 20 and stratified by country (Denmark or Norway) and clinician (general practitioner, physiotherapist, chiropractor, or outpatient clinic).

### **Intervention**

The SELFBACK intervention is an app-delivered, evidence-based decision support system that, guided by case-based reasoning, provides weekly, individually tailored self-management recommendations for three main components that are endorsed by clinical guidelines: (1) physical activity (number of steps), (2) strength and flexibility exercises, and (3) daily educational messages. In addition, the app provides general information about LBP and access to several tools (goal setting, mindfulness audios, pain-relieving exercises, and sleep reminders) that participants could use at their convenience in addition to usual care.

Randomised to receive usual care, participants were instructed to manage their LBP according to the advice or treatment offered by their clinician. No restrictions or limitations were put on usual care. Having a common practice comparator (usual care) and inclusion of people with co-occurring musculoskeletal pain and multimorbidity together with no upper age limit makes the setting more naturalistic, which improves generalizability and hence makes the data more suitable for cost-effectiveness evaluation.

### **The SELFBACK system and user involvement**

The SELFBACK system was developed through the involvement of key stakeholders (care-seekers and healthcare professionals) to ensure face validity. The content of the SELFBACK system was established using an intervention mapping process, and the app was tested in a pilot and a feasibility study before the RCT.

### **Patient self-reported data**

Data on self-reported measures were collected in the SELFBACK trial using an online tool at baseline, 6 weeks and 3, 6 and 9 months after the inclusion in the trial. Data used from the questionnaires for this current analysis are socio-demographic characteristics, quality of life measured by EQ5D-5L, Roland-Morris disability questionnaire for LBP-related disability, self-efficacy by the Pain Self Efficacy Questionnaire and variables adjusted for in the main trial

(clinical setting of recruitment [General Practitioner, Physiotherapist, Chiropractor, Outpatient back clinic], age [years], sex [female, male], education [ $<10$  years,  $10\text{--}12$  years,  $>12$  years], duration of current pain episode at baseline [ $\leq 4$  weeks,  $5\text{--}12$  weeks,  $> 12$  weeks] and average pain intensity in the preceding week at baseline [0-10 scale]).

### Economic evaluation

This cost-effectiveness analysis will be conducted from a national healthcare perspective and a limited societal perspective including effects on formal productivity. We merge individual self-reported patient data with Danish national registries. An overview of databases and costs is provided in Table 2.

## Outcome variables

### Effectiveness measures

For the cost-effectiveness analysis, we will use two clinically relevant outcomes; 1) the main outcome from the SELFBACK trial, which is LBP-related disability measured by RMDQ and 2) self-efficacy reflecting people's confidence in carrying out specific activities despite their pain and indirectly how they self-manage, measured by the Pain Self-Efficacy Questionnaire (PSEQ).

### Utility measure

For the cost-utility analysis, we will use quality-adjusted life years (QALYs) as the primary outcome. QALYs are calculated based on the EuroQol-5L Dimension questionnaire (EQ-5D) and weighted according to the Danish value set status. EQ-5D is the most common instrument for cost-effectiveness analyses. The 9-month QALYs will be calculated by multiplying the utilities by the amount of time a patient spent in a particular health state. Transitions between health states are linearly interpolated.

### Measures of resource use and costs

In Denmark, the Danish National Health Service primarily finance the cost of healthcare utilisation in primary and secondary healthcare. Exceptions to this are chiropractic, physiotherapy, and psychology consultations in primary care, which incur additional out-of-pocket expenses the patient pays.

Individual patient data on primary sector healthcare utilisation and related cost are retrieved from the National Health Service Registry (Sygesikringsregisteret) with services provided by General practitioners, Chiropractors, Physiotherapists, and Medical specialists. Use of secondary sector care utilisation will be retrieved from the National Patient Registry (Landspatientregisteret), including assessments, tests and procedures at Spine centers and rheumatology, neurology, orthopaedic and neurosurgery departments and redeemed prescriptive medication from the National Prescription Registry (Lægemiddeldatabasen).

Costs of prescription medication will be calculated based on prices charged by the pharmacies (excluding VAT). Primary healthcare costs will be valued according to the prevailing fee schedules agreed upon between the providers and the Danish Regions. Hospital treatment costs will be valued with official hospital Diagnosis Related Group (DRG) tariffs provided by the National Health Data Authority. All monetary values will be presented in euros at 2022

cost levels. Therefore, costs will be uplifted to 2022 price levels using the Net Price Index maintained by Statistics Denmark.

#### Formal productivity costs

Data on lost formal production, measured in terms of long-term (>4 weeks) sickness absence, will be retrieved from the Danish Register for Evaluation of Marginalization (DREAM). Productivity loss was estimated using the Human Capital method based on weeks of absence from work for participants who were not retired. The value of forgone earnings is assessed by the average gross wage.

#### Intervention costs

Valuation of the SELFBACK intervention will be based on average marked values of similar apps. Since all costs and outcomes occur within 1 year, discounting will not be applied.

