If randomised to a) the selfBACK DSS in addition to usual care, participants are given wearable device along with instructions and assistance on how to download, install and pair the wearable device with the app and how to connect the apps on the smartphone (see section 3.2.1). Moreover, the participant is given information about their follow-up assessments and information on how to contact the researcher if needed. If a participant declines participation at the face-to-face meeting, the researcher will ensure that the information from the baseline questionnaire is deleted.

If randomised to b) usual care, participants are instructed on the principles of usual care, and are given the same information as the selfBACK intervention group about the follow-up assessments and how to get in touch with the researcher if needed.

The flow of participants through the trial is described in **Figure 1**.

[figure not shown]

Figure 1: Participant flow through selfBACK trial. Abbreviations: GP: general practitioner, PT: physiotherapist, C: chiropractor, HCP: Health care provider, LBP: Low Back Pain

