2.6. Randomisation

Participants are randomised to either a) selfBACK DSS in addition to usual care or b) usual care only. The randomisation is performed as a block randomisation with permuted blocks of random size unknown to the research team and stratified by country and care provider (i.e. general practitioner, physiotherapist,

chiropractor, or Spine Centre). The allocation ratio between the SELFBACK DSS in addition to usual care and the usual care groups is 1:1. Randomisation will be performed by a web-based randomisation system (Web Case Report Form; WebCRF) developed and administered by Unit of Applied Clinical Research, Faculty of Medicine and Health Sciences, NTNU, Trondheim, Norway. This unit is not otherwise involved in the trial management or trial conduct. A contractual agreement has been signed with the Unit of Applied Clinical Research concerning their role and responsibilities in the project. The WebCRF system will hold a minimal data set on all screened participants (variables include: a trial id number, country, care provider, recruitment site, age, gender).

2.7. *Blinding*

The study is a single-blinded study. Participants are not blinded to group allocation. The analysis and interpretation of the study results will be performed by researchers blinded to group allocation. Once the study is completed, a copy of the data will be extracted in pseudonymised form for statistical analyses. All personal information that may lead back to specific participants (i.e. e-mail address, username etc.) will be removed from the data. The information concerning group allocation will be added to the dataset with the intervention and control group randomly labelled as A and B. The randomisation key (i.e. document entailing information on which group is which) is kept at the Unit of Applied Clinical Research at NTNU. They will provide the randomisation key to the research team once a blinded interpretation of the results is finalized (see section 5.2).

3. Interventions

3.1. *Usual care*

Participants randomised to usual care will follow any diagnostic or treatment-related pathway (e.g. receive information, advice or treatment) as instructed by their HCP. They are also allowed to seek care, treatment or help elsewhere as normal. After the completion of the trial at 9 months, participants who have completed all follow-up assessments are contacted and offered a wearable device similar to the SELFBACK intervention group.

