3.2. *SELFBACK in addition to usual care*

The SELFBACK intervention is a digital DSS for self-management of LBP provided to the participant via a smartphone app (SELFBACK app) [26]. In addition, the participant is provided with a wearable device (i.e., a step-detecting wristband) that interacts with the SELFBACK app. Based on the step count and participant's self-reported data, the SELFBACK app provides individually tailored self-management plans including educational messages, physical activity advice and exercise recommendations matched to the participant's health status, as generated by the DSS. Importantly, the intervention is not intended to replace follow-up by HCPs, but to supplement the ordinary care by the HCP, and the participant is informed accordingly. Thus, participants randomised to the SELFBACK intervention may continue to seek care, treatment or help as normal.

Stakeholder and user involvement are increasingly seen as essential especially in the context of complex interventions. It is seen as important to enhance engagement, empowerment and to maximize long-term sustainability. User involvement has been a key feature during the development of the selfBACK system and the design of trial procedures. We have had direct input from patients through a range of mechanisms that are described elsewhere [26]. The content of the intervention was developed using

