3.2.1. The digital DSS

The selfBACK system constitutes a data-driven predictive DSS that uses the Case-Based Reasoning (CBR) methodology [29] to capture and reuse participant cases in order to suggest the most suitable self-management plan for participants. The data sources for the CBR system comprise 1) the initial participant data collected by the baseline web-based questionnaire, 2) a weekly report by the participant in the selfBACK app (including pain, function, fear-avoidance, workability, sleep, self-efficacy, stress, health belief and barriers), and 3) the step-detecting wearable. On a weekly basis, this information is used to revise the self-management plan by matching the characteristics of the current participant case with existing successful participant cases in the selfBACK case-base. The weekly tailoring questions will only be given if relevant for the participant. As an example, if a participant has indicated sleep problems at baseline, then a tailoring question will be asked in appropriate time-intervals, and, based on the answer, a set of educational messages on e.g. sleep hygiene will be offered to the participant. Consequently, the DSS will deliver an individualised self-management plan for the coming week via the selfBACK app. All interaction between the participant and the selfBACK DSS happens via the selfBACK app. There is no interaction between the DSS and HCPs. The architecture of the DSS and the interaction between the participant, the wearable device, the selfBACK app and the database is outlined in Figure 2. A full description of the DSS is published elsewhere [30].

[figure not shown]

Figure 2: Overview of the selfBACK decision support system.

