3.2.1. Wearable device and supporting apps

The Xiaomi Mi Band 3 wristband is used to track number of steps. The step count is synchronized with the GoogleFit app on Android devices and Apple HealthKit app on iOS devices throughout the day. The wristband registers movement in all three planes (frontal, horizontal and sagittal) via an ADI (Analog Devices, Inc.) ultra-low power acceleration sensor and computes step-count from this information. It connects to the phone via Bluetooth (V4.2 BLE) and requires Android 4.4+ / iOS 9.0+.¹ The wearable device is to be worn on the participant's wrist continuously while participating in the intervention but could be taken off during sleep and water-based activities. To connect the wristband and step count function to the selfBACK app, the MiFit app is required to be installed on the participant's smartphone. Additionally, Apple HealthKit needs to be activated on iOS devices, and GoogleFit needs to be activated or downloaded if not preinstalled on Android devices. The three apps (i.e., MiFit, Apple HealthKit and GoogleFit) are freely available, and can be downloaded without cost for the participant. An account needs to be created for the apps for every participant. An installation guide has been developed to help participants install and connect apps, and a researcher will be present at the time of installation to ensure the correct setup.

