3.2.4. Access, frequency and mode of delivery

The participants access their self-management plan via the selfBACK app and enter data into the DSS by answering tailoring questions in the app and by wearing the connected wearable device. These data are combined with the participant self-reported outcome as outlined in Figure 2. The participant is encouraged to use the selfBACK app daily or at least once a week, in order to be offered a new self-management plan. The app will send push-notifications reminding the participant to open the app and view the new self-management plan. The participant can disable or adjust the frequency of notifications in the app settings. The goal of the intervention is that participants learn to self-manage their LBP, which may potentially result in participants discontinuing their use of the app. Consequently, discontinuation is not necessarily a sign of low compliance but may indicate a high self-management level.

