3.3. Ancillary and post-trial management

All participants randomised to the selfBACK intervention can continue their use of the wearable device after the trial. However, their access to the selfBACK app will cease after the 9 months follow-up, by disabling the participants username, thereby restricting login to the app. All participants randomised to the usual care group are offered a wearable device after completing all follow-up assessments. No further post-trial management is planned.

4. Outcomes

All outcomes are collected at baseline, six weeks, three, six and nine months. Additionally, participant characteristics and demographic variables are collected at baseline. Participant characteristics include age, gender, height, weight, and relevant comorbidities. The demographic variables include family relations, ethnicity, educational status, employment, and work characteristics if employed. The outcomes included in the trial were based on recommendations for LBP trials [40-42].

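### In the supplied text the SAP costs SELFBACK from app prices alone, so the wristband given to the intervention arm falls outside base-case incremental cost unless Table 2 or those prices cover it

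*SAP*

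**What the plan says.** **SAP.** The Intervention costs section has a single valuation rule: "Valuation of the SELFBACK intervention will be based on average marked values of similar apps". I read the word before 'values' as 'market'. The Intervention section describes an app-delivered system and lists step counts among its components, but no supplied SAP section names a wristband. The Cost-effectiveness section plans a deterministic sensitivity analysis on the app's valuation, with no stated range. The opening of Section 4 commits to counting all costs in both arms over the nine months. The Economic evaluation section refers to Table 2 for an overview of databases and costs; that table is not in the supplied text.

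**Protocol.** The wristband is part of what the intervention arm receives:
- Section 2.5, on allocation to SELFBACK: "participants are given wearable device along with instructions and assistance on how to download, install and pair the wearable device with the app".
- Section 3.2: "In addition, the participant is provided with a wearable device (i.e., a step-detecting wristband) that interacts with the SELFBACK app".
- Section 3.2.1 (The digital DSS), the last of three data sources for the system: "and 3) the step-detecting wearable".
- Section 3.2.4, on how participants "enter data into the DSS by answering tailoring questions in the app and by wearing the connected wearable device".

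Controls get access later. Under Section 3.1, once the trial ends at nine months, "participants who have completed all follow-up assessments are contacted and offered a wearable device similar to the SELFBACK intervention group". Section 3.3 repeats this timing.

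**The concern.** The mean additional cost per patient is the SAP's first objective. A resource used by one arm only, inside the costing window, belongs in that difference. If it has no unit cost and no data source, it enters as zero.

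Such an omission is not sampling noise. It lowers the cost of every intervention participant who received the device by the same amount, so it shifts the point estimate and the cost coordinate of every bootstrap replicate together. Neither the bootstrap nor the acceptability curve would reveal it. With the app value held fixed, the error always favours SELFBACK.

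As the text stands, one analyst could apply the app-price rule literally while another could add the device on the strength of the commitment to count all costs. They would report different base cases from the same registered plan.

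**Working it through.** The plan states no intervention cost, so there is no figure to reproduce. The check compares the texts and then scales the result.

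**Step 1. Is the device used in one arm only within the window?** Yes. It is supplied at allocation (Protocol 2.5) and is meant to be worn throughout participation, apart from sleep and water-based activities (Protocol 3.2.1, Wearable device and supporting apps). Controls are offered one only after completing follow-up (3.1, 3.3).

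**Step 2. Would another SAP cost source pick it up?** No.
- Measures of resource use and costs draws on registers of primary care, hospital care and redeemed prescriptions.
- Formal productivity costs uses long-term sickness absence.
- Neither would record a device handed out by researchers.

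**Step 3. Are there other uncosted items of this kind?** The companion software is not one: "The three apps (i.e., MiFit, Apple HealthKit and GoogleFit) are freely available, and can be downloaded without cost for the participant". The wristband is the physical item that an app price may miss.

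**Step 4. Effect on the ICER.** The SAP defines the ICER as the mean cost difference divided by the mean effect difference. Write ΔC for the cost difference without the device, ΔE for the effect difference, and c for the device cost charged per participant. Assume that every intervention participant received a device.

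- Device left out: ΔC / ΔE
- Device included: (ΔC + c) / ΔE
- Shift: c / ΔE, which for ΔE > 0 makes the ICER without the device too low

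**Step 5. Scale.** The documents give neither c nor ΔE. The values below are assumptions that show a range; they are not estimates.

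| Assumed c (euros) | ΔE = 0.005 QALY | 0.01 | 0.02 | 0.05 |
|---|---|---|---|---|
| 20 | 4,000 | 2,000 | 1,000 | 400 |
| 30 | 6,000 | 3,000 | 1,500 | 600 |
| 50 | 10,000 | 5,000 | 2,500 | 1,000 |
| 100 | 20,000 | 10,000 | 5,000 | 2,000 |

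Entries are c / ΔE in euros per QALY; for example 30 / 0.01 = 3,000.

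For the disability outcome, c = 30 with assumed RMDQ differences of 2 and 1 points gives 30 / 2 = 15 and 30 / 1 = 30 euros per point.

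**Step 6. Full price or a share.** Protocol 3.3 states: "All participants randomised to the selfBACK intervention can continue their use of the wearable device after the trial". Charging only the nine-month share of a device with a life of L years multiplies c by 0.75 / L. With c = 30 and an assumed L of 3 years, the charge is 30 × 0.75 / 3 = 7.50 euros. At 0.01 QALY the shift becomes 7.50 / 0.01 = 750 euros per QALY instead of 3,000. The charging rule therefore matters as much as the price.

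**The case against.** **Table 2 may list the device.** It is the natural place for such a line, and text absent from the supplied copy cannot be treated as absent from the plan. This stands, and the point is conditional on it. If Table 2 does list the device, what remains is a cross-reference.

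**The app-price rule may be meant for the whole package.** Its subject is the intervention, not the app, and a market-price proxy for a bundle is a legitimate choice. If the comparator apps are sold with a tracker, nothing is missing. But the rule does not say so, and the sensitivity analysis refers to the app's valuation, which favours the narrower reading.

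**The commitment to count all costs may cover the device.** It sets the scope but supplies no source or unit price, so an analyst would have to invent both.

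Three stronger readings are tempting, and the documents do not support them:
- *That the SAP has decided to exclude the wristband.* It makes no such statement; the supplied text is silent.
- *That total intervention cost is understated on balance.* The app price is itself a proxy and could be too high or too low. The shortfall of c holds only with the app value fixed.
- *That the effect is known to be negligible, or known to change the conclusion.* Without a device price, a cost SD or a QALY gain, neither can be shown. The SAP's remark that the trial was not powered for cost-effectiveness says nothing about the size of c.

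**Conclusion.** The concern holds in conditional form and is minor. In the supplied text, the stated rule yields a base case priced on apps alone and leaves out a resource that only the intervention arm uses within the nine months. Unless Table 2 lists the wristband or the similar-app prices include one, incremental cost is too low by c with the app value fixed, and the ICER is off by c divided by the incremental effect.

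The direction rests on the text and simple algebra, given a positive incremental effect. The size rests wholly on assumed inputs: 400 to 20,000 euros per QALY across 20 to 100 euros and 0.005 to 0.05 QALY at full price, and less if only a nine-month share is charged. The width of that range mostly reflects what the documents do not give. No bound is claimed on the movement of the acceptability curve, because that also needs a cost SD.

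**What to change.** Check Table 2 first. If it already lists the wristband, cite it in the Intervention costs section. If the similar-app prices already include a step tracker, say so there and add nothing.

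Otherwise, make two changes:
1. In Intervention costs, define the base-case intervention cost as the app value plus the wristband unit price. Give the source of the price, and state whether the full price or a nine-month share is charged (with the assumed device life if a share). The SAP's existing rule on 2022 price levels then applies.
2. In Cost-effectiveness, run the deterministic sensitivity analysis on this total, not on the app value alone, and state the range.

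The cost is a sentence or two, one unit price to obtain, and an ICER slightly less favourable to SELFBACK. No new participant data are needed.
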